### 7.8.2 Continuous malaria indicator survey to assess malaria parasite prevalence

#### 7.8.2.1.1 *Main trial*

The continuous malaria indicator survey (cMIS), conducted under a separate protocol, provides adequate power to detect a 30% reduction in the all-age malaria prevalence detected by RDTs per year from 29.0% to 20.3%. The 29% prevalence is based on the observed all-age prevalence in Rarieda sub-county (29%) (representing two-thirds of the study area) and in Alego-Usonga (47.3%), representing one-third of the study area. The 47.3% in Alego-Usonga is based on cMIS data in neighbouring Karemo. The prevalence estimate in Rarieda is reduced from 29% to 27.7% to account for a 50% drop in malaria prevalence in children < 5 years of age who will receive the RTS,S vaccine. Because this age group only represents 13.9% of the population, the anticipated impact of RTS,S on the all-age prevalence in Rarieda is modest. The pooled estimate of the RTS,S adjusted all-age prevalence of 27.7% in Rarieda and 47.3% in Aleg-Usonga is 34.1%. We propose to use a more conservative prevalence of 29% to allow a 15% reduction in malaria prevalence due to annual variations in environmental conditions (e.g. rainfall, temperature) ( $0.85 \times 34.1\% = 29\%$ ). This requires 3,520 participants per year (44 per cluster, including 9 non-responders and 35 responders) (ICC=0.05, power=90%, two-sided alpha=0.05, and assuming 20% non-responders, e.g. refusals, not at home, etc.). The values for the intra-cluster correlation (ICC), parasite prevalence, and non-response rates were estimated from the ongoing cMIS study. Where possible, households that are included in the first year will be excluded in the second year. Over 2-years, and assuming no overlap in participants between the first and second year, a sample size of 88 per clusters (including 18 non-responders and 70 responders) would provide 80% power to detect a 23.7% reduction or 90% to detect a 27.3% reduction (ICC=0.05, alpha=0.05). Similarly, 70 responders per cluster after two years would provide 80% power to detect a 30% reduction if the ICC is 0.091 instead of 0.05, or 90% power if the ICC is 0.064.

#### 7.8.2.2 *Baseline*

A similar annual sample size of 44 per cluster, including 9 non-responders and 35 responders, will be used in 100 clusters during the baseline year before the deployment of ATSBs in the intervention arms.

### 7.8.3 Entomological monitoring

Twelve intervention clusters and 12 control clusters will be selected for entomological monitoring. Based on previous field research in Mali, large reductions in mosquito density are anticipated, up to 90% (although density reductions may be dependent on the season due to seasonal fluctuations in abundance). A minimum reduction in density of 50% was used for sample size calculation.

Ten 10 entomological collections per cluster per month are required to detect a 50% reduction in mosquito densities per CDC UV light trap (two-sided alpha=0.05, power=80%, ICC=0.38, 24 clusters

[12 per arm]). For the impact of ATSBs on parity or sporozoite rates, all unfed mosquitoes captured alive will be used to estimate parity rates. All Anopheles mosquitoes collected during the study will be subjected to ELISA to estimate sporozoite infection rates.

#### 7.8.4 Rapid ethnographic methods

Focus group discussions (FGD) and in-depth interview (IDI) will be implemented at three discrete time periods: 1) before ATSB deployment, 2) at least one month after the first round of ATSB deployment, and 3) at least one month after a subsequent ATSB deployment. Each FGD will involve six to eight participants. FGDs will be segregated by sex and community members versus monitoring assistants. In the pre-ATSB deployment stage a total of six FGDs will be conducted; four among community members and two among monitoring assistants. In each of the post-ATSB deployment rounds, twelve FGDs will be conducted among community members and two among monitoring assistants. IDIs will be conducted among community residents. A total of eight will be conducted in the pre-ATSB deployment period, and then twelve each during the post-deployment rounds.

## 8 METHODS: ASSIGNMENT OF INTERVENTIONS

### 8.1 ALLOCATION AND RANDOMIZATION

Restricted randomization will be used to allocate 80 of the 100 baseline clusters to intervention and control arms for the main trial to minimize any imbalance between study arms on key baseline characteristics. The steps to achieve restricted randomization will be conducted by a study team member who is not responsible for trial implementation. The steps are as follows:

1. Establish balance criteria. The factors described in the table below may be considered for suitability as restriction criteria.
2. Generate a list of at least 100,000 randomizations
3. Check randomizations against balance criteria and drop those that do not fit
4. Assess the number of randomizations left. There may be a need to relax criteria and start again if fewer than 10,000 acceptable randomizations remain.
5. Test remaining set of potential randomizations for validity, specifically that all clusters are being independently assigned to study arms (e.g. check that no two clusters are always jointly assigned to the same arm).
6. Randomly choose a randomisation.
7. Flip a coin to determine if arm A or arm B is ATSB or control.
8. Step 6 and 7 to be done in public with community participation.

Table 3: Factors to consider for restricted randomisation

Covariable/ endpoint	Restriction criteria	Data source	Analytic method
Malaria disease incidence	The difference in mean clinical case incidence between trial arms (size of difference to be assessed when data are available)	Baseline cohort	The difference in disease incidence of cluster summaries between study arms
Bednet use	The difference in mean proportion of persons slept under any net night before survey between trial arms $\leq 5$ percentage points	Baseline survey	The difference in means of cluster summaries of the proportion of persons of all ages slept under any net night before survey between arms

Population	The total population size of the larger trial arm is no more than 10% larger than the smaller arm	Enumeration datasets	Sum(pop size of clusters Arm large)/Sum(Pop size of clusters arm Small) less than 1.10
RTS,S/AS01 vaccinating area	Number of clusters in intervention and control arm balanced by vaccinating or non-vaccinating areas for RTS,S/AS01	Kenya National Vaccinations and Immunizations Programme (NVIP)	N in Arm A == N in Arm B
Housing density*	The difference in mean housing density between trial arms $\leq 0.3$ SD of overall cluster level housing density	Enumeration + cluster boundaries GIS files Or Remotely sensed data (GRUMP/WorldPop) plus Cluster boundaries GIS	$SD(\text{cluster estimates of housing densities}) * 0.3 \geq  \text{mean}(\text{cluster estimates housing density Arm a}) - \text{mean}(\text{Cluster estimates of housing density Arm b}) $
HF location	Number of clusters with a primary care facility exactly balanced across arms	Study team documentation	N in arm A == N of Arm B
Altitude	Differences in mean altitude of cluster centroids between trial arms $\leq 0.3$ SD of overall cluster level mean altitude	Digital Elevation Model (ASTER) combined with (GIS) shapefiles for cluster boundaries.	$SD(\text{cluster estimates of altitude}) * 0.3 \geq  \text{mean}(\text{cluster estimates of altitude Arm a}) - \text{mean}(\text{Cluster estimates of altitude Arm b}) $
Entomological data collection	The number of clusters with entomological data collection planned is exactly equal across study arms	Study team self-report	N in arm A == N in arm B

\*Either urbanization or housing density will be selected; these variables are likely collinear.

## 8.2 BLINDING

Allocation of study arms will not be blinded to the participants, the deliverers of the intervention, or the main investigators. Sham ATSBs will not be deployed in control areas because it is logistically not feasible to produce the number of ATSB stations needed for both intervention and control arm. The potential for bias among operator-dependent mosquito catches (indoor and outdoor aspirations) will be minimized using a standardized protocol. Additionally, the potential for bias in mosquito catches using CDC light traps is very low. The potential for changes in human behaviour affecting malaria control intervention coverage, namely LLIN use, will be minimized through comprehensive community engagement and communications. LLIN use will be promoted in intervention and control areas. Additionally, study teams will monitor LLIN use in intervention and control areas to document changes throughout the life of the study. Laboratory processing of mosquito and human blood specimens will be blinded.

To further minimize bias, we will use an objective primary outcome measure and mask all laboratory staff to the treatment assignment of individual participants. The trial statistician will also be blinded regarding the allocation arm when the statistical analysis plan is developed and the analytical syntax is written, which will be validated and completed using dummy randomization codes. The actual

allocation will only be provided to the study team after locking the database and approval of the statistical analysis plan by the independent DSMB before they review any trial results.

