## 5 OBJECTIVES AND OUTCOMES

Table 1: Objectives and outcomes

5.1 PRIMARY OBJECTIVE AND OUTCOME	
Primary objective	Primary endpoint
To determine if ATSB deployment plus universal LLIN coverage is superior to universal LLIN coverage alone in reducing the case burden of clinical malaria in western Kenya	
 
The incidence rate of clinical malaria by the end of year-2, defined as current fever (axillary temperature of <math>\geq 37.5^{\circ}\text{C}</math>) or history of fever in last 48 hours and a positive rapid diagnostic test (RDT, pLDH or HRP2), in children aged 1-<15 years enrolled in the cohort study
 

5.2 SECONDARY OBJECTIVES AND OUTCOMES	
5.2.1 Efficacy	
Secondary objectives	Secondary endpoints
To determine if ATSB deployment plus universal LLIN coverage compared to universal LLIN coverage alone is superior in reducing malaria infection	
 
The time to first malaria infection assessed by PCR by the end of year-2, in children aged 1-<15 years enrolled in a cohort study
 
The incidence rate of malaria infection detected by RDT (pLDH) by the end of year-2, in children aged 1-<15 years enrolled in a cohort study
 
The prevalence of malaria infection diagnosed by RDT in continuous household surveys in participants aged <math>\geq 1</math> month.
 

To determine in ATSB deployment plus universal LLIN coverage compared to universal LLIN coverage alone reduces the clinical case burden in health facilities and communities	
 
The incidence rate of RDT or microscopy confirmed clinical malaria assessed through passive surveillance at health facilities and community-based surveillance by Community Health Volunteers serving the village-clusters
 

To determine if the rate of overall illness events differs in the ATSB deployment plus universal LLIN coverage arm when compared to the control arm	
 
The incidence rate of non-malaria illness in the cohort study
 
The incidence rate of all-cause sick visits assessed through passive surveillance at health facilities and community-based surveillance by community health volunteers
 

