### 7.1 STUDY SITE

The study will be performed in Rarieda and Alego-Usonga sub-Counties of Siaya County, western Kenya. Malaria transmission is moderate to high and occurs year-round with peaks in June and July, and November and December following the long and short rains, respectively. Annual parasite prevalence from the continuous malaria indicator survey is estimated to be 36.5% by RDT among children under five years of age (unpublished data). In Siaya County, confirmed malaria incidence by passive case detection for 2016 was 585 per 1,000 population, and clinical (unconfirmed) malaria incidence rate was 261/1,000 (DHIS2 dashboard for Siaya County). The primary malaria vectors are *Anopheles funestus* and *An. arabiensis*. *An. gambiae s.s.* is a secondary vector. Malaria vector resistance to pyrethroid insecticides is documented in Kenya.

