- Two weeks after the enrolment visit, the household will be visited and a finger-prick blood sample (~250 $\mu$ L to 1mL) will be drawn to prepare five dried blood spots, and to prepare a blood smear for parasite clearance confirmation.
- If the participant is febrile at this visit, the staff member will review the RDT result from the enrolment visit.
  - If the enrolment visit RDT was negative, the participant will be re-tested with an RDT and if positive, the participant will be ineligible for the cohort and second-line antimalarial treatment will be administered as per national guidelines (e.g. dihydroartemisinin-piperaquine). If the RDT administered during this visit is negative, we will proceed with the blood smear.
  - If the enrolment visit RDT was positive, the blood smear will be expedited.
- If the participant is found to be positive for malaria by microscopy, we will consider the participant ineligible for the cohort and will withdraw him/her. A staff member will return to the house to convey this information and provide second-line antimalarial treatment as per national guidelines (e.g. dihydroartemisinin-piperaquine).

9.1.2.3 *At each monthly cohort visit (starting 4 weeks after enrolment)*

- Prior to each follow-up visit, the cohort study team will call cohort members to remind them of the next visit and reschedule, if necessary, to minimize loss to follow-up. Up to three visits will be made to each cohort study household to complete a follow-up visit.
- At each of these visits, a finger finger-prick blood sample (~250 $\mu$ L to 1mL) will be drawn to prepare approximately five dried blood spots for testing, as indicated in the enrolment visit.
- If the participant has an axillary temperature of  $\geq 37.5^{\circ}$  C or reported history of fever in the last 48 hours, a malaria RDT will be performed using blood from the same fingerprick. Those who test positive for malaria by RDT will be treated at the household according to the Kenya Ministry of Health Guidelines unless they already received appropriate antimalarial treatment from other sources in the previous seven days. Cohort members who do not have objective fevers or report a history of fever in the last 48 hours will not be tested for malaria by RDT.

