- For women of childbearing age, pregnancy status will be evaluated as described in the enrolment visit section. Those in whom a pregnancy test is indicated but who decline and those who have a positive pregnancy test will be withdrawn from the cohort. These women

may opt to be visited and evaluated for malaria, free of charge for the duration that they would have been in the cohort.

- A questionnaire will be administered on a tablet or smartphone to the participant or his/her parent/guardian, including questions about the history of recent illness (including AEs and SAEs), care-seeking, LLIN use, and travel and commuting history. If the cohort member sought care between scheduled visits, we will copy any relevant information from these health records to evaluate any malaria diagnostics performed and antimalarial treatment given
- A follow-up visit in four weeks time may be scheduled at this time. Parents/guardians and the participant will be reminded to call the study staff at the number provided on the consent form if the participant becomes ill before the next scheduled visit.
- The limited care provided by the study team includes any care related to study procedures, malaria illness, or other uncomplicated acute illnesses such as acute respiratory or gastrointestinal disease. The study will not be responsible for the care of pre-existing conditions or chronic or traumatic conditions diagnosed during the trial.

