### 9.4.3 Analysis of the primary outcome

#### 9.4.3.1 Definition of events and person-time to obtain incidence rates

The primary outcome analysis will be based on a comparison of the unadjusted (crude) incidence rates between study arms using a multi-level (variance compartments model). The incidence rate will be defined as the total number of incident clinical malaria cases divided by the total person-time observed among each cohort.

The person-time (i.e., the denominator) and events (i.e., the numerator) will be defined as follows:

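### Section 8.2 counts an objective primary outcome among its protections against bias, but reported fever can trigger the RDT and qualify an event, so unequal reporting in this open-label trial can move the IRR either way

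*Protocol*

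**What the plan says.** On masking, protocol section 8.2 states: "Allocation of study arms will not be blinded to the participants, the deliverers of the intervention, or the main investigators". Sham stations are ruled out as logistically not feasible. Section 8.2 then lists protections: standardised mosquito catches, promotion and monitoring of net use, masked laboratory staff, a statistician masked while the analysis plan and code are written, and the statement that "we will use an objective primary outcome measure".

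The outcome is defined in section 5.1 and repeated in 6.1: a measured axillary temperature of at least 37.5 °C, or "history of fever in last 48 hours and a positive rapid diagnostic test (RDT, pLDH or HRP2"). Either fever route is sufficient.

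Section 9.1.2.3 (monthly cohort visits) sets the testing rule. Children who "do not have objective fevers or report a history of fever in the last 48 hours will not be tested for malaria by RDT". Between visits, families are "reminded to call the study staff at the number provided on the consent form if the participant becomes ill", so sick visits start with the family (9.1.2.4).

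The primary analysis (9.4.3.1) is "based on a comparison of the unadjusted (crude) incidence rates between study arms".

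**The concern.** An outcome that is independent of what unmasked people say is a sound protection in an open-label trial. Here the protection is claimed, but the definition does not provide it. For a child without measured fever, what the caregiver or child says decides whether a test is done at a monthly visit at all. Families in the intervention arm have bait stations on their outer walls.

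The positive RDT limits the problem without removing it. Where infection is common, an additional reported fever can turn a coincidental infection into a counted event. RDT prevalence at the site is "estimated to be 36.5% by RDT among children under five years of age" (7.1), and section 9.4.3.1.3 itself warns that HRP2 antigen can persist for weeks after an infection has cleared.

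At stake is the primary IRR. More reporting in control villages, or less in ATSB villages, imitates efficacy. The opposite pattern conceals it.

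**Working it through.** **1. The texts side by side.** Section 8.2 says objective. Sections 5.1 and 6.1 accept a reported history of fever. Section 9.1.2.3 uses the word objective for measured fever in order to set it apart from reported fever, so the protocol draws the distinction that 8.2 overlooks. The masking in 8.2 covers laboratory staff, but the qualifying RDT is done by field staff at the household (6.3.3.1, 9.1.2.3). PCR enters the primary event definition only at the visit after a treated episode (9.4.3.1.3).

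The fever condition is exact for monthly visits. At enrolment everyone is tested (9.1.2.1), and at sick visits tests follow clinical indication (9.1.2.4).

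**2. The plan's own figures.** From section 7.8.1.1: control rate 0.845 and intervention rate 0.592 per person-year, 40 clusters per arm, 22 analysed person-years per cluster, CV 0.4, two-sided alpha 0.049.
- Control events: 0.845 × 880 = 743.6; the protocol gives 744.
- Clusters per arm, from (z for alpha/2 + z for power)² × [(0.845 + 0.592)/22 + 0.4² × (0.845² + 0.592²)] / (0.845 − 0.592)²: 38.9, or 39.9 with the usual one added. The protocol has 40, and power comes to 90.1-90.8% against the stated 90%.

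The design reproduces. On the log scale, SE(log IRR) = √{[1/(22 × rate₀) + 1/(22 × rate₁) + 2 × 0.4²]/40}. With no effect this is 0.103, so an observed IRR below about 0.816 is significant.

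**3. Excess reporting in the control arm, product without effect.** Assumed, not in the protocol: reported fever at 2 extra percentage points of monthly visits, of which 10-34% are RDT-positive. The upper end borrows the pooled all-age prevalence of 34.1% in section 7.8.2.
- Extra events per person-year: 12 × 0.02 × 0.10 = 0.024; 12 × 0.02 × 0.34 = 0.082.
- Observed IRR: 0.845/(0.845 + 0.024) = 0.97; 0.845/(0.845 + 0.082) = 0.91.
- Chance of a falsely significant benefit, with the SE formula above: about 4.5% and 14%, against 2.45% nominal in that direction.

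**4. The same excess in the ATSB arm, true reduction 30%.**
- Observed IRR: (0.592 + 0.024)/0.845 = 0.73; (0.592 + 0.082)/0.845 = 0.80.
- Power on the log scale: about 85% and 58%, against 92% without bias.

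**5. What it would take for bias alone to reach significance.** Let s be the share of events resting on reported fever alone and r the relative under-reporting in the ATSB arm. Observed IRR = true IRR × (1 − s × r). A null product crosses 0.816 only if s × r exceeds about 0.18, for example s = 0.7 with r above 26%. The protocol gives neither s nor r.

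**6. Planned outcomes that escape the fever condition.**
- PCR time to first infection in the cohort (5.2.1, 9.4.4.1.2): blood spots are taken at every monthly visit and laboratory processing is blinded.
- RDT prevalence in the continuous malaria indicator survey (cMIS): 6.3.3.3 and 9.1.3.2 state no fever condition. Section 9.3.1, which treats cohort and survey sampling together, reads as if fever triggered the RDT in both, and should be aligned.
- Non-malaria illness rate in the cohort (5.2.1): it depends on reporting, which is why it can reveal a difference in reporting.

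The cohort rate of infection by RDT is not an independent check, because at monthly visits it passes through the same condition.

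**The case against.** The strongest reply is that the protocol already contains ways to recognise reporting bias. A lower primary IRR without movement in PCR infection, survey prevalence or the entomological outcomes, or with a parallel shift in non-malaria illness, would point to reporting rather than efficacy. This stands. A reader might infer that nothing in the plan guards against the bias, or that it could not be told from efficacy; the documents do not support that. What remains is that these outcomes check the primary IRR without correcting it, and that the protocol nowhere links them to this purpose.

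Second, sensitivity models and tables by arm commonly sit in the SAP, which is not at hand. This also stands: their absence from the protocol is not the finding. The finding is the property that 8.2 claims; the analysis is part of the remedy.

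Third, the size is assumed. The 2-point excess and the 10% have no source in the protocol. The 34% is a community figure for all ages, whereas cohort children are treated at enrolment and withdrawn if the two-week smear is positive, so it is probably too high. The sum also treats every extra event as additive, although treatment may pre-empt a later episode and two weeks of person-time are removed. All of this stands.

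Fourth, a reader might infer that the bias favours ATSB. Nothing in the protocol fixes a direction. Intervention households have monthly monitoring contact (7.6.1.3), which could raise reporting there. Control clusters receive sensitisation on care-seeking (7.6.1.2), and messages on net use and care-seeking are meant to be similar across arms (9.1.7).

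**Conclusion.** The point holds as an error in what section 8.2 states. The primary outcome is RDT-confirmed, but it rests on measured or reported fever. It is not objective in the sense needed to offset open-label allocation, and laboratory masking does not reach the household test. No stated analysis of the primary endpoint addresses this: the per-protocol, covariate-adjusted and subgroup analyses in 9.4.2 and 9.4.3 do not bear on it.

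Size and direction cannot be established from the protocol. Under the labelled assumptions the shift is moderate: a null IRR reads 0.97-0.91, which does not reach the significance threshold of about 0.816, or a true 0.70 reads 0.73-0.80. It would not by itself make an ineffective product appear to reach the 30% target, but it could distort an estimate near the reduction that section 6.2.1 treats as the minimum for a WHO recommendation.

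**What to change.** - In 8.2, replace the word objective with: RDT-confirmed, with measured or reported fever. Acknowledge that fever reporting is unmasked.
- Name PCR time to first infection, cMIS RDT prevalence and the cohort non-malaria illness rate as the checks on reporting bias.
- Pre-specify, in the protocol or SAP, a sensitivity analysis of the primary model that counts only events at scheduled monthly visits with measured temperature of 37.5 °C or more and a positive RDT. The limit to scheduled visits matters because sick visits, even with measured fever, depend on families calling.
- Tabulate by arm the tests done on reported fever alone and their positivity.

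The primary definition and the clinical procedures stay unchanged. The data are already collected, so the work is one extra model and one table. The downside is fewer events and wider intervals in the sensitivity analysis, which should be read for consistency with the primary IRR and not as a second test of efficacy.
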